#### 9.1.1 Primary Analysis

The primary objective is to compare the efficacy of naldemedine 1.25 mg, 2.5 mg, and 5 mg and placebo for the primary endpoint.

Let  $\hat{\mu}_{kg}(t)$  be the estimate of RMST at time  $t$  for the surgical procedure  $k$  ( $k=1,2,3$ ) and treatment group  $g$  ( $g=1,2,3,4$ ). Let  $\hat{\mu}_k(t) = (\hat{\mu}_{k1}(t), \hat{\mu}_{k2}(t), \hat{\mu}_{k3}(t), \hat{\mu}_{k4}(t))^T$  be the vector of estimates of RMST for surgical procedure  $k$ .  $c = (-3, -1, 1, 3)^T$  is defined as contrast coefficient. The null hypothesis will be

$$H_0: c^T \mu_1(t) = c^T \mu_2(t) = c^T \mu_3(t) = 0$$

and test statistics  $T$  will be

$$T = \frac{\sum_{k=1}^3 c^T \hat{\mu}_k(t)}{\sqrt{\sum_{k=1}^3 \{Var[c^T \hat{\mu}_k(t)]\}}}$$

, where

$$Var[c^T \hat{\mu}_k(t)] = 9 * Var[\hat{\mu}_{k1}(t)] + 1 * Var[\hat{\mu}_{k2}(t)] + 1 * Var[\hat{\mu}_{k3}(t)] + 9 * Var[\hat{\mu}_{k4}(t)]$$

Therefore p-value will be

$$2\{1 - \Phi(|T^{obs}|)\}$$

, where  $\Phi(\cdot)$  will be standard normal distribution and  $T^{obs}$  will be the observed test statistics.

For pairwise comparison between treatment groups i and j (i, j = 1, 2, 3, 4), the null hypothesis will be

$$H_0: \mu_{1i}(t) - \mu_{1j}(t) = \mu_{2i}(t) - \mu_{2j}(t) = \mu_{3i}(t) - \mu_{3j}(t) = 0$$

and test statistics S will be

$$S = \frac{\sum_{k=1}^3 \{\hat{\mu}_{ki}(t) - \hat{\mu}_{kj}(t)\}}{\sqrt{\sum_{k=1}^3 \{Var[\hat{\mu}_{ki}(t)] + Var[\hat{\mu}_{kj}(t)]\}}}$$

- 1) The mean survival time, which is also referred to as the RMST, of GI2 events within 240 hours will be estimated using the area under the Kaplan-Meier (KM) curve. To demonstrate the linear dose-response relationship between treatment groups (3 naldemedine groups and placebo group) and the RMST, the linear contrast test for trend with contrast coefficients of (-3, -1, 1, 3) will be performed based on the test statistics T described above. Two types of KM curve with 95% confidence bound and point estimate line only will be provided. SAS code will be provided in section 13.2.
- 2) Pairwise comparisons of all treatments will be undertaken based on the test statistics S described above and the differences of treatment means including their 95% confidence interval (CI) will be calculated as

$$\frac{1}{3} \sum_{k=1}^3 \{\hat{\mu}_{ki}(t) - \hat{\mu}_{kj}(t)\} \pm z_{\alpha/2} \times \frac{1}{3} \sqrt{\sum_{k=1}^3 \{Var[\hat{\mu}_{ki}(t)] + Var[\hat{\mu}_{kj}(t)]\}}$$

$z_{\alpha/2}$  is the upper  $100\alpha\%$  quantile of the standard normal distribution.

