4.2 Scientific Rationale for Study Design

Prolonged hospitalization due to delay in return of GI function after bowel surgery may increase patient exposure to such risks as hospital-acquired infection and deep vein thrombosis, as well as increase healthcare costs. As described in [Section 2.2](#), there is a need for a pharmacologic agent with an improved benefit/risk profile that can be administered to patients who are undergoing bowel resection and bowel transection.

The current study (Study 1902G1721) with naldemedine (which is approved in the US for the treatment of OIC in adult patients with chronic noncancer pain, including patients with chronic pain related to prior cancer or its treatment who do not require frequent [eg, weekly] opioid dosage escalation), will be conducted to determine whether naldemedine can accelerate the time to upper and lower GI recovery following surgeries that include partial bowel resection with primary anastomosis and radical cystectomy with bowel transection and primary anastomosis.

This study employs a standard interventional clinical study design and will be conducted at multiple hospitals. The design of this study allows assessment of the efficacy, safety, and tolerability of naldemedine administered orally by ODT at 3 different doses compared with placebo in patients undergoing partial small or large bowel resection with primary anastomosis or radical cystectomy requiring bowel transection with primary anastomosis.

The randomization and stratification for this study (Section 6.3) allows for a well-balanced distribution of patients across treatment groups and will help determine whether there is a dose response to allow the choice of the most effective dose. The double-blind, placebo-controlled design was chosen because blinding of patients and investigators/study personnel helps to prevent bias and the inclusion of placebo is appropriate for use in this patient population.

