9. STATISTICAL CONSIDERATIONS

9.1 Statistical Hypotheses

The study design and primary objective are based on the hypothesis that naldemedine 1.25 mg, 2.5 mg, and/or 5 mg are superior to placebo for patients undergoing surgeries that include a bowel resection or bowel transection.

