9.4 Statistical Analyses

The detailed statistical analysis methods will be specified in the separate SAP. Changes from analyses outlined in the protocol will be detailed and justified in the SAP. The initial SAP will have a version 1.0 available by first patient randomized and will be finalized before unblinding/database lock. The SAP will be finalized before scheduled database lock. This section is a summary of the planned statistical analyses of the primary and secondary endpoints.

For programming and analysis purposes, the protocol study days will be mapped as shown in [Table 9-1](#).

Table 9-1 **Mapping Information for Study Days**

Protocol Day	Screening Period	Treatment Period								Follow-up Period	
	Day -14 to 0	Day 0		Day 1	Day 2	Day 3	Day 4	Days 5 to 10	Day of Discharge	Early Termination	
	Baseline	Before Surgery	After Surgery								
Mapped Analysis Day	Day -14 to 1	Day 1 Before Surgery (surgery day)	Day 1 After Surgery (surgery day)	Day 2 (Postop Day 1)	Day 3 (Postop Day 2)	Day 4 (Postop Day 3)	Day 5 (Postop Day 4)	Days 6 to 11 (Postop Days 5 to 10)	Day of Discharge	Early Termination	End-of-study Visit

Postop = postoperative

Unless otherwise noted, continuous variables will be summarized by using the number of non-missing observations, arithmetic mean, standard deviation (SD), median, minimum, and maximum values as descriptive statistics; categorical variables will be summarized by using the frequency count and the percentage of patients in each category as descriptive statistics.

Patient study data, including data not appearing in tables, will be presented in by-patient data listings. In general, all tables and graphs will be presented by treatment group. Pharmacokinetic data and any derived data will be listed. All analyses and tabulations will be performed by using SAS Version 9.2 or higher, and Phoenix WinNonlin Version 6.2.1 or higher.

If statistical tests are performed, they will be performed at the 0.05 significance level using 2-sided tests, except where otherwise noted. No multiplicity adjustment of statistical tests will be applied in this study. Missing data will not be replaced.

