9.4.5.1 Primary Efficacy Endpoint

The primary endpoint will be time from the end of surgery (defined as the time the patient leaves the operating room) to time to first toleration of solid food (defined as the time when the patient consumes a meal that requires chewing and has no significant nausea or vomiting, as per the judgment of the investigator, for 4 hours after that solid food) and first bowel movement (GI2).

The mean survival time, which is also referred to as the RMST, of GI2 events within 240 hours will be estimated using the area under the Kaplan-Meier (KM) curve. To demonstrate the linear dose-response relationship between treatment groups (3 naldemedine groups and placebo group) and the RMST, the linear contrast test for trend with contrast coefficients of (-3, -1, 1, 3) will be performed. If a dose-response relationship is detected, then pairwise comparisons of the RMST between each dose group of naldemedine and the placebo group will be conducted, and the treatment differences (with its 95% confidence interval [CI]) will be provided. If an event does not occur during the evaluation period of 240 hours, the patient will be censored at the time of his/her last nonmissing postbaseline assessment. The same analysis will be performed in the Per Protocol set. In addition, the reason for discharge prior to having the first bowel movement will be listed.

Patients will continue to be evaluated for efficacy regardless of treatment adherence. The use of additional therapies or interventions that could treat any component of the primary endpoint (eg, motility agents, anti-emetics, laxatives, etc), may confound the results of the primary efficacy analysis. This list of therapies will be finalized before database lock. To examine this issue, the following exploratory analyses of the GI2 endpoint will be performed or provided:

- Repeat of the primary analysis, excluding all patients who received additional therapies at any time postrandomization that could treat any of the components of the GI2 endpoint. It is recognized that this subset is selected based on postrandomization decisions, may be confounded with the treatment group, and may not represent a randomized subgroup of the primary endpoint.
- Table of proportion of patients in each treatment group who received additional therapies that could treat any of the GI2 components.

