9.4.5.2 Secondary Efficacy Endpoints

Secondary efficacy endpoints will be as follows:

- Time from the end of surgery (as defined for the primary endpoint) to time when the discharge order is written
- Proportion of patients requiring postoperative reinsertion of the nasogastric tube
- Proportion of patients with nausea on Days 1 through 3
- Proportion of patients with vomiting on Days 1 through 3
- Proportion of patients discharged by Day 10 who are readmitted for any reason within 30 days after discharge from the hospital

For time from the end of surgery to time when the discharge order is written, the same KM approach as used for the primary efficacy analysis will be performed. The proportion of patients for each of the other parameters will be summarized by treatment group.

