## 6.2 Statistical Testing

All statistical tests will be performed at the 2-sided significance level of 0.05, unless otherwise noted. No multiplicity adjustment will be made in this study.

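### The SAP runs all six pairwise RMST comparisons unconditionally, where the protocol allows only three dose-versus-placebo comparisons after a positive trend test, and the SAP gives no justification for the change

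*SAP*

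**What the plan says.** **Protocol.** Section 9.4.5.1 runs the linear contrast test with coefficients (-3, -1, 1, 3) on the RMST to 240 hours. It then sets a condition: "If a dose-response relationship is detected, then pairwise comparisons of the RMST between each dose group of naldemedine and the placebo group" follow, each with a difference and 95% CI. Section 9.4 leaves detailed methods to the SAP but adds: "Changes from analyses outlined in the protocol will be detailed and justified in the SAP".

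**SAP.** Section 9.1.1 item 1 runs the same contrast through the statistic T. Item 2 then says: "Pairwise comparisons of all treatments will be undertaken based on the test statistics S described above". The statistic S is defined for groups i and j that each run from 1 to 4. Nothing in item 2 refers to the result of item 1. SAP Section 1 names protocol Version 3 of 18 June 2020, so the SAP was written for the same protocol text.

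**Multiplicity.** Protocol 9.4: "No multiplicity adjustment of statistical tests will be applied in this study". SAP 6.2: "No multiplicity adjustment will be made in this study".

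**Time to discharge order.** Protocol 9.4.5.2 says that for time until the "discharge order is written, the same KM approach as used for the primary efficacy analysis will be performed". SAP 9.2.1.1 mentions only pairwise comparison, done as in 9.1.1.

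**The concern.** The two documents give different rules for the step after the trend test. If T is not significant and one dose has p < 0.05 against placebo, the protocol does not make that comparison, while the SAP makes it and reports a p-value.

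This matters because the hypothesis in protocol 9.1 is that "naldemedine 1.25 mg, 2.5 mg, and/or 5 mg are superior to placebo", and protocol 4.2 says the design "will help determine whether there is a dose response to allow the choice of the most effective dose". Dose-level results will therefore be read closely. If the conflict is settled after unblinding, the choice of rule can follow the result.

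The usual safeguard would not catch it. SAP Section 1 promises that departures from the final SAP will be documented in the study report, but an ungated comparison complies with the SAP.

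**Working it through.** **1. Number of comparisons.** Four groups give 4 × 3 / 2 = 6 pairs: three dose-versus-placebo and three dose-versus-dose. The protocol names the first three only.

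**2. Justification.** The SAP contents list has no section on changes from the protocol, and no SAP text supplied mentions this change.

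**3. Set-up for the size.** Take four independent arm estimates with equal variance, normal and unstratified. A pair is significant if |difference| / (√2 × SE) > 1.96. The trend test is significant if |c'x| / (√20 × SE) > 1.96, where c = (-3, -1, 1, 3) and c'c = 9 + 1 + 1 + 9 = 20. Simulations used 4,000,000 draws per scenario.

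**4. The plan's own figures (44 and 85 per group, 80% power).** The Weibull parameters are not given, so these cannot be reproduced exactly. The SD can be back-solved:
- 24 h: arm means 0, 8, 16, 24 give a contrast of -8 + 16 + 72 = 80. Arm SE = 80 / (√20 × 2.802) = 6.385 h, and SD = 6.385 × √44 = 42.4 h.
- 18 h: the contrast is 60. Arm SE = 60 / (√20 × 2.802) = 4.789 h, and SD = 4.789 × √85 = 44.2 h.

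The two SDs are close but not equal, because a Weibull variance changes with the mean. One assumed Weibull case (placebo RMST 120 h, shape 3, 20% censored) gives 44.9 and 83.8 per group, so 44 and 85 are plausible. The SD is an assumption below, shown at both values.

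**5. Global null** (no SD needed).

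| Event | Ungated | Gated by T |
|---|---|---|
| At least one of 3 doses falsely better than placebo | 6.3% | 2.0% |
| Any of the 3 dose-versus-placebo pairs significant, either direction | 12.5% | 4.0% |
| Any of the 6 pairs significant | 20.3% | 4.5% |

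The trend test itself rejects in 5.0%. A dose-versus-placebo pair is significant while T is not in about 12.5% - 4.0% = 8.5% of trials, or about 4.3% counting only the favourable direction. Adding the dose-versus-dose pairs without a gate raises the any-pair rate by 20.3% - 12.5% = 7.8 points, but those are not efficacy claims against placebo.

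**6. Real effects: favourable dose-versus-placebo p < 0.05 while T fails.**

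| Reductions at 1.25 / 2.5 / 5 mg | SD 42.4 h: n = 44 / 85 | SD 44.2 h: n = 44 / 85 |
|---|---|---|
| Linear 8 / 16 / 24 h (planned shape) | 4.2% / 0.7% | 4.8% / 1.0% |
| Only 5 mg works, 24 h | 6.9% / 2.5% | 7.2% / 3.1% |
| Plateau 24 / 24 / 24 h | 22.0% / 5.8% | 23.8% / 7.5% |

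**7. Effect of strata.** SAP 9.1.1 weights the three surgical strata equally. With strata of 10%, 70% and 20% (an assumption), the SE rises by √[(1/0.1 + 1/0.7 + 1/0.2) / 9] = 1.35. The linear figure at 44 per group then lies between 7% and 8% instead of 4.2%. The null figures in step 5 do not depend on the SE.

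**The case against.** The best case for leaving the text alone is that this is a Phase 2 dose-finding trial, that protocol 9.4 delegates detail to the SAP, and that both documents disclaim multiplicity adjustment. Under the SAP wording every pair is computed whatever T shows, so the SAP itself leaves no choice of tests after unblinding. The and/or hypothesis and the dose-selection aim also fit ungated comparisons. The gate is weak protection in any case: if only 5 mg works, a lower dose is falsely superior in 4.5% of trials ungated and 4.3% gated at 44 per group.

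Most of this stands as a limit on weight, and it may be a good reason to choose ungated comparisons. It does not remove the conflict. A disclaimer of alpha adjustment does not cancel an explicit if-then condition, and delegation of detail comes with a duty to justify changes.

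Three stronger readings might be inferred, and the documents do not support them.
- *The trial's type I error control is broken.* Neither document promises family-wise control, and the trend test uses the same contrast and alpha in both.
- *Discharge readiness and actual discharge have separate defects, which multiply the number of extra tests.* SAP 9.3.1.1 and 9.3.2.1 refer back to 9.1.1, which includes T. They lack a gate only because 9.1.1 lacks one. Whether the protocol's shared Kaplan-Meier approach includes the condition is open, so a test count across endpoints would rest on an assumed reading.
- *The documents would usually disagree.* That needs a dose-response that reverses at the top dose, which no section assumes.

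**Conclusion.** The point holds. SAP 9.1.1 item 2 differs from protocol 9.4.5.1 in both condition and number of pairs, and the justification required by protocol 9.4 is absent. The consequence is limited to whether a dose-versus-placebo result may be tested and reported as superiority after a failed trend test.

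The size is modest under the planned shape: about 4% of trials at 44 per group and 0.7% at 85. It is larger if the response is flat across doses (22% and 6% for a 24-hour plateau). Under the global null, false superiority of at least one dose is 6.3% ungated and 2.0% gated. The non-null figures rest on a back-solved SD and an unstratified equal-variance approximation; unequal strata would change them.

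The change should be made before unblinding, but it is a correction to wording and does not put the primary analysis in doubt.

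**What to change.** **Default.** Make SAP 9.1.1 item 2 follow the protocol, for example: *If T is significant at two-sided 0.05, each naldemedine dose will be compared with placebo using S, with the difference and 95% CI.*

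**If more is wanted.** If the sponsor wants dose-versus-dose comparisons, or any estimates when T is not significant, the SAP should add them as a stated and justified departure under protocol 9.4. They should be reported as descriptive, with nominal CIs and p-values, and not as superiority findings. Estimates after a failed trend test do need this step, because protocol 9.4.5.1 makes the differences and CIs conditional as well as the tests.

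**Other endpoints.** SAP 9.3.1.1 and 9.3.2.1 inherit the corrected rule through their reference to 9.1.1. SAP 9.2.1.1 names pairwise comparison only, so it should say whether that endpoint's own trend test is run first.

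**Cost.** A few sentences of SAP text. The SAP is Version 1, and protocol 9.4 foresees finalization before unblinding. The gate lowers the chance of a formal dose finding when the response is not linear: with SD 42.4 h and a 24-hour plateau, any-dose power falls from 93.0% to 71.0% at 44 per group and from 99.6% to 93.9% at 85. Under the linear shape at 44 per group, power for 5 mg falls only from 75.7% to 73.7%. The protocol's own rule already carries this cost.

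### SAP 9.1.1 calls the pairwise RMST-difference interval a 95% interval but defines its multiplier as the upper 100α% normal quantile, which is 1.645 at α = 0.05, not 1.960

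*SAP*

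**What the plan says.** SAP Section 9.1.1, item 2, says that "the differences of treatment means including their 95% confidence interval (CI) will be calculated as" the average over the three surgical-procedure strata of the RMST difference, plus or minus z_{α/2} times one third of the root of the summed stratum variances. The sentence directly below the formula says that z_{α/2} "is the upper $100\alpha\%$ quantile of the standard normal distribution".

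The level is fixed elsewhere. SAP Section 6.2: "All statistical tests will be performed at the 2-sided significance level of 0.05, unless otherwise noted". Protocol Section 9.4, on statistical tests: "they will be performed at the 0.05 significance level using 2-sided tests, except where otherwise noted". Protocol Section 9.4.5.1 gives the same confidence level for the pairwise results: "the treatment differences (with its 95% confidence interval [CI]) will be provided". Neither document gives α any other value for this analysis.

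The code printed in SAP Section 13.2 obtains the stratum RMSTs and their standard deviations and says that T and S are calculated from them. It shows no confidence interval and no critical value.

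**The concern.** The label and the definition cannot both be followed. The 95% label and the α/2 subscript call for the upper 2.5% point of the standard normal. The explanatory sentence, read with α = 0.05, gives the upper 5% point.

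What is at stake is the width of the reported error bars. SAP Section 9.1.1 applies the formula to all pairs of the four groups, which is 4 × 3 / 2 = 6 pairs for each endpoint. Section 9.1.2 repeats the primary analysis twice: in the Per-protocol Set, and after excluding patients who received additional therapies. Sections 9.2.1.1, 9.3.1.1 and 9.3.2.1 send the discharge-order, discharge-readiness and actual-discharge comparisons back to Section 9.1.1. A literal reading would make every one of these intervals too narrow, and some would exclude zero beside a paired test that is not significant at 0.05. No multiplicity adjustment is planned, so readers comparing doses will lean on these intervals.

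**Working it through.** **Inputs**
- α = 0.05, two-sided (SAP 6.2; Protocol 9.4).
- Stated confidence level 95% (SAP 9.1.1, item 2; Protocol 9.4.5.1).
- Interval D ± m × SE, where D = (1/3) Σ_k (μ̂_ki − μ̂_kj) and SE = (1/3) √Σ_k {Var[μ̂_ki] + Var[μ̂_kj]} (SAP 9.1.1).
- Two-sided p-value 2{1 − Φ(|T|)}. SAP 9.1.1 writes this for the trend statistic T only. I assume the same form for the pairwise statistic S, as the two-sided level in Section 6.2 implies.

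**Step 1: reproduce the 95%.** Under normality, coverage is 2Φ(m) − 1.

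| Reading of the multiplier | m | Coverage | Two-sided p at the boundary |
|---|---|---|---|
| Upper 100(α/2)% point, α = 0.05 | 1.960 | 95.0% | 0.05 |
| Upper 100α% point as written, α = 0.05 | 1.645 | 90.0% | 0.10 |
| Upper 100α% point as written, α = 0.025 | 1.960 | 95.0% | 0.05 |

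The first row reproduces the plan's label and the second does not. The third does so only by giving α a value that the documents never state and that conflicts with SAP 6.2.

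**Step 2: width.** 1.645 / 1.960 = 0.839, so the literal interval is about 16% too narrow. The correct interval is 1 / 0.839 = 1.19 times as wide.

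**Step 3: agreement with the paired test.** The factor 1/3 cancels, so D / SE = S. The interval excludes zero exactly when |S| > m. With m = 1.645 this happens whenever p < 0.10. The paired test is significant at 0.05 only when |S| > 1.960. The two therefore disagree for 1.645 < |S| < 1.960, that is, for p between 0.05 and 0.10. For a pair with no true difference, the probability of landing there is 0.10 − 0.05 = 0.05.

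**Step 4: check with the stratified estimator.** A simulation of the three-stratum average, with 1,000,000 draws and assumed stratum standard errors of 20, 8 and 12 h, gave coverage of 0.900 with 1.645 and 0.950 with 1.960. Those standard errors are illustrative. Under normality the coverage does not depend on them.

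**The case against.** The strongest reply is that a competent programmer would use 1.960. The interval is called 95% in both documents, the formula carries the subscript α/2, testing is two-sided at 0.05, and the p-value for T is written as two-sided. Against all this stands one explanatory sentence, which is most likely a wording slip. That argument stands as to intent. It does not remove the contradiction in the text.

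A reader might infer more than the documents support:
- **That the trial will report 90% intervals.** This follows only if the sentence is followed over the label, the subscript and the protocol.
- **That the sentence alone determines the multiplier.** It does not. The label, the subscript and the two-sided level bear on it too, and all three point to 1.960.
- **That the primary test is affected.** T, S and their p-values do not use z_{α/2}, so neither the trend test nor its power changes.
- **That the narrowing can be put in hours.** The documents state no standard deviation. The sample-size simulation is described by Weibull event times and about 20% censoring, without parameters. The standard error in the formula is built from stratum variances, and the expected stratum sizes are not given. Only the ratio and the coverage can be stated.

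A lost /2 in the reading of the typeset mathematics cannot be wholly excluded, although the α/2 subscript at the start of the same sentence is intact. A check against the signed SAP would settle it.

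Finally, a literal implementation would probably be noticed whenever an interval excluding zero appeared beside p > 0.05. That lowers the risk, but only when some pair falls in the band. Otherwise the intervals would be too narrow with nothing to show it.

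**Conclusion.** The definition is wrong as written, and the point is minor. SAP Section 9.1.1 contradicts itself on the multiplier for the pairwise RMST-difference interval, and the explanatory sentence is the part in error.

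If that sentence were followed, coverage would be 90.0% instead of 95%, the width would be 0.839 of the correct one, and the interval would exclude zero for any pair with p between 0.05 and 0.10. These figures rest on α = 0.05 two-sided, on the normal approximation that the SAP already uses, and, for the last, on S having the same two-sided p-value form as T. They do not depend on sample size, standard deviation or stratum mix. The consequence is conditional on literal programming and is confined to interval limits.

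**What to change.** Replace the sentence below the interval formula in SAP Section 9.1.1 with: z_{α/2} denotes the upper 100(α/2)% point of the standard normal, equal to 1.960 for α = 0.05.

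The later sections that refer back to Section 9.1.1 then need no edit. The cost is one sentence in the SAP, made before database lock and unblinding. No design element, data collection, test or p-value changes.
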